Design Overview. In this factorial experiment (see Table 1), participants (not willing to enter cessation treatment at the time of enrollment) recruited by phone after initial outreach or primary care visits in or telemedicine appointments with participating clinics in UW Health and AdvocateAurora Health will be screened, consented, and randomized over the phone to one of 16 conditions resulting from the crossing of the 4 experimental factors in this 2 (incentives on vs. off) x 2 (tailored vs. generic outreach letters) x 2 (care manager calls on vs. off) x 2 (access to intensive treatment on vs. off) design. Participants who request treatment for smoking cessation over the next 2 years will do so through a Tobacco Care Manager who will coordinate referrals to a tobacco quitline (the Wisconsin Tobacco Quit Line (WTQL) for Wisconsin residents) and/or the patient's primary care provider, as preferred by the patient in the standard care conditions. Tobacco Care Managers will also coordinate scheduling with a UW-CTRI Health Counselor for intensive smoking cessation treatment. Participants will have access to either standard or intensive smoking cessation treatment for 24 months, and will receive outreach promoting smoking cessation twice per year from enrollment to 22 months post-enrollment. Participants will be asked to complete brief (10-20-minute) follow-up telephone interviews 6, 12, 18, and 24 months after enrollment. Those claiming abstinence at the 12- and 24-month post-enrollment phone interviews will be asked to return to their primary care clinic to complete breath, urine, and/or saliva testing to verify abstinence from combustible tobacco. This will entail providing breath samples for carbon monoxide testing and/or a urine or saliva sample for immediate cotinine/anabasine testing (no samples will be stored). Participants may also be asked to collect a saliva sample at home and return it in the mail. If a participant sets a target stop-smoking date as part of a smoking cessation treatment episode (either standard or intensive treatment), the participant will be asked to complete telephone follow-up interviews 3, 12, and 26 weeks post-target-quit-day, as well. Participation in the study will last 24 months (27 months maximum, if the person is not reached immediately for the final 24-month post-enrollment telephone follow-up or visit). In addition, data on health status and healthcare utilization for participants who do vs. do not use stop-smoking treatment and quit smoking will be extracted from the EHR for up to 1 year pre-enrollment, and 4 years post-enrollment to inform economic analyses for Aim 3 and moderation analyses for Aim 4.

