For those randomized to access to intensive treatment, the Tobacco Care Manager or UW-CTRI staffer will obtain oral assent to screen for current eligibility for varenicline and/or combination NRT (depending on their initial eligibility at enrollment—only the medications(s) for which the person met prerequisites at enrollment will be considered as options), will conduct this screening, and will then obtain oral consent to begin intensive treatment over the phone (see uploaded Treatment Initiation Screen and Consent). Those who were randomly assigned to receive incentives for treatment initiation will be reminded that they can earn \$40 by completing a first counseling call with a UW-CTRI quit coach. Medication and UW-CTRI health-counselor delivered telephone counseling will not be dispensed to patients unless they provide oral consent for intensive treatment. Medications also will not be dispensed until the patient's primary care provider has had a chance to review and decline a request for the patient to begin the medications for which they are eligible according to the study protocol. Because we: anticipate that not all participants will request smoking cessation treatment during the study, want medication screening to be done at the time of the smoking cessation attempt, and want to minimize burden on primary care providers, medication requests for combination NRT or varenicline will be sent to primary care providers only after a participant has requested intensive treatment, assented to and passed eligibility screening, and consented to intensive treatment over the phone. Those in the intensive treatment condition who are not eligible for either combination NRT or varenicline will still have access to 3 sessions of UW-CTRI quit coach counseling, as will those who are eligible but decline to use combination NRT or varenicline. Access to counseling is not dependent on medication eligibility or election. Adverse events will be assessed among all those who initiate stop-smoking treatment at phone follow-up interviews 3, 12, and 26 weeks post-target quit date. In addition, adverse events will be assessed among those in intensive treatment during the quit coach counseling calls 1 week pre-quit, 1 day post-quit, and 1 week post-quit.

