3. Post-quit attempt assessment (See uploaded Post Treatment Follow-Up assessment). Those who request smoking cessation treatment through a Care Manager will be asked to complete 10-20 minute telephone interviews 3, 12, and 26 weeks post-target-quit day and paid \$10 for these calls (this payment is low to avoid interfering with the incentive manipulation). At these follow-ups, patient self-report of smoking, treatment use, and quitting attitudes, beliefs, and experiences (including withdrawal and social support related to quitting) will be assessed, along with any adverse events that occurred since the beginning of cessation treatment. In addition, participant utilization of treatment will be assessed by tracking how many calls or visits the participant completed and how much medication they report using.

To enhance intervention fidelity, intervention delivery will be assessed via supervisory review of recorded motivational interventions by the Care Manager and smoking cessation counseling calls delivered by UW-CTRI Health Counselors, with feedback regarding performance to enhance fidelity, as needed.

To enhance follow-up interview and visit completion rates, participants will be texted, mailed, sent MyChart reminders or automated phone calls (depending on their communication preferences as noted in the EHR and during enrollment).

Data management, transmission and storage

Data will be transferred from the EHR to research databases for use in tailoring and personalizing outreach (as randomly assigned) and tracking recruitment, participant healthcare utilization, smoking cessation treatment, and changes in smoking status, insurance type, or health status over the course of the 2-year study. Both healthcare systems maintain secure, HIPAA-compliant electronic health records for their operations and have mechanisms and processes in place to extract and encrypt data from the EHR for research purposes. Staff at UW-CTRI will receive data on enrollees who have provided consent for such data sharing as

part of the oral consent process. The data to be extracted from the EHR for the purposes of reach-focused interventions and assessment are shown in the uploaded List of EHR Data to Be Extracted. The research office will also receive data from the Wisconsin Tobacco Quit Line regarding services those in Standard Care received (i.e., did they complete the counseling call, were they sent any smoking cessation medications).

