Aim 1. To develop an optimized package of health system interventions to promote smoking cessation treatment reach among patients not initially willing to quit, logistic regression analyses will be conducted with binary treatment initiation over 1 year of study enrollment as the primary outcome, in the primary sample randomized on all 4 experimental factors. Effect size estimates will be generated and all main and all 2-way, 3-way, and 4-way interactive effects will be tested as predictors in the logistic regression model. In addition, the magnitude of the difference in treatment initiation rates between the most promising intervention conditions and the cell in which all the intervention components are off will be used to generate an upper limit estimate of optimized reach intervention package effects. Exploratory analyses will be conducted adjusted for covariates known to be predictive of treatment use. Exploratory sensitivity analyses will be conducted to estimate intervention component effects across a range of assumptions regarding missing outcome data. We anticipate that 25% of follow-up data will be missing and will examine the robustness of results across intent-to-treat and less stringent assumptions regarding missingness (i.e., that 90%, 80%, or 70% of missing cases are smoking) in sensitivity analyses. We may also use multiple imputation and examine the consistency of results across multiply imputed datasets and those imputed using the simple methods already described. This analysis will use data collected via UW-CTRI staff during follow-up telephone interviews supplemented by data regarding smoking cessation attempts and treatment utilization extracted from the EHR and the WTQL.

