Communication with patients via the MyChart patient portal will likewise be conducted in HIPAA-compliant ways that conform to healthcare system standards. A unique study ID will be used to store all data on individual participants and information linking that study ID to participant identifying information will be maintained by the data manager. Data being used for analysis will be identified with the study ID only. Participant contact information will only be available to study staff having direct contact with participants. Data will be stripped of direct identifiers (limited datasets) or completely de-identified prior to sharing with others outside the IRB-approved research team.

To protect against violations of privacy, patients will first have the option to opt out of the program, at study launch and quarterly thereafter, at the clinic. Those who opt out will not receive a call from a Tobacco Care Manager for recruiting and offers of smoking cessation treatment. In addition, potentially sensitive information from the EHR (e.g., depression or substance use status) will not be used to tailor automated outreach letters among those who consent to participation in this study. Only demographic and care team information will be used for tailoring and personalization.

If, in the course of the study, participants reveal important clinical information to their Tobacco Care Manager (e.g., during motivational intervention calls), the Care Manager, who will be an employee of the healthcare system, will be able to communicate directly with the patient's

primary care team (e.g., if a patient notes that they are coughing up blood) via the EHR and will advise the patient to seek care from their care team or emergency care, as appropriate.

Routine adverse event assessment will not occur in this study, except in the context of smoking cessation treatment episodes, given the minimal and informational nature of the health system reach interventions and research assessments. Adverse events that occur during smoking cessation treatment will be assessed during post-quit-day follow-ups (3, 12, and 26 weeks post-quit day). Adverse events reported by patients will be assessed fully and reported to the IRB, the host healthcare system, and if appropriate (i.e., if serious or necessitating a change in the protocol) to the study sponsor and FDA, in a timely manner, as specified by pertinent guidelines and regulations.

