Plans for assuring compliance with requirements regarding the reporting of adverse events. This DSMP requires that investigators notify NIH and the University of Wisconsin IRB in a timely manner (consistent with IRB and NIH policies) of the occurrence of any SAE or any AE which is severe, unexpected, and possibly related to study medication or protocol. Any adverse, study-related events that come to light during the study will be assessed fully and reported. If an SAE might be related to study drug use, both the Food and Drug Administration (FDA) and the manufacturer will be notified within 5 days of investigators becoming aware of the event. Examples of SAEs would be untoward medical or intervention occurrences that result in death, are life-threatening, require hospitalization or prolonging of existing hospitalization, create persistent or significant disability/incapacity, or involve congenital abnormality/birth defects. Unanticipated problems will be monitored and reported to the DSMC. These are events that meet the following criteria: 1) suggest the research places subjects or others at increased risk of harm, 2) are unexpected (in terms of nature, severity or frequency) given the research procedures that are described in the study-related documents, and 3) possibly related to study participation. Any SAE will be queried and reported if it meets the definition of unanticipated problem. All study-related adverse events will be assessed in a timely manner so that NIH, FDA, and the IRB may be notified, as needed. Adverse event assessment, recording, reporting, and investigation will be accomplished through staff training, structured/standardized assessments of untoward occurrences/events, and regular monitoring by the study team. The PL and PIs have ultimate responsibility for ensuring that SAEs are reported in a timely manner. Additionally, the IRB will receive an annual report of all SAEs and AEs meeting the criteria listed above.

Plans for assuring that any action resulting in a temporary or permanent suspension of an NIH-funded clinical trial is reported to the NIH grant program director responsible for the grant. The NIH grant program director will be notified within 5 days if the PI deems it necessary to suspend the clinical trial. In the case of a temporary suspension, the PI and PL will develop a plan for continuation of the study and discuss this plan with the NIH grant program director in a reasonable time frame.

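### Death, hospitalization and birth defects are named as serious adverse events, but no systematic way of finding them is described beyond participants' own reports by phone

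*Combined protocol and SAP*

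**What the plan says.** Section H (the answer on how risks will be minimized) limits the scope of active assessment: "Routine adverse event assessment will not occur in this study, except in the context of smoking cessation treatment episodes". For those episodes it then gives the timing: "Adverse events that occur during smoking cessation treatment will be assessed during post-quit-day follow-ups (3, 12, and 26 weeks post-quit day". Section B (Consent) sets the calls: "Adverse events will be assessed among all those who initiate stop-smoking treatment at phone follow-up interviews 3, 12, and 26 weeks post-target quit date". It adds three contacts in one condition: "adverse events will be assessed among those in intensive treatment during the quit coach counseling calls 1 week pre-quit, 1 day post-quit, and 1 week" after the quit day. The Assessment Plan, item 3, gives the recall period of the post-quit interviews. They ask about smoking and treatment use, "along with any adverse events that occurred since the beginning of cessation treatment".

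The Data Safety and Monitoring Plan defines SAEs to include death and life-threatening events, and events that "require hospitalization or prolonging of existing hospitalization, create persistent or significant disability/incapacity, or involve congenital abnormality/birth defects". It also says that events reported at any Care Manager contact or follow-up assessment will be assessed and passed on. The Data and Safety Monitoring Committee (DSMC) reviews safety every six months, overall and by treatment condition.

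EHR data have several stated uses. In the Design Overview, health status and utilization data "will be extracted from the EHR for up to 1 year pre-enrollment, and 4 years post-enrollment to inform economic analyses for Aim 3". The other purpose given there is the study of moderators under Aim 4. The Assessment Plan, item 2, has EHR and pharmacy utilization data extracted at each semi-annual follow-up. The data management section also uses EHR data to track utilization and changes in health status during the study. None of these places names the finding of SAEs as a use.

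On missing data, the Analysis Plan for Aim 1 states: "We anticipate that 25% of follow-up data will be missing".

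**The concern.** The SAE definition and the means of finding SAEs do not match. The definition covers events that remove or impair the person who is meant to report them. Someone who has died cannot answer a call, and someone seriously ill may plausibly be less likely to. Loss of this kind depends on the event, so it does not behave like ordinary missing data.

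The DSMC has to judge undue risk from what reaches it, and expedited reporting to the FDA and the manufacturer starts only when investigators become aware of an event. With a revised target of 240–300 participants in the experimental sample, of whom only those who start treatment are actively assessed, SAEs will be few and losing even one could matter. The utilization data that would show hospitalizations in the two health systems are already to be extracted.

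**Working it through.** The plan states no detection rate for SAEs, so there is no figure to reproduce. Its timing figures are consistent: 98 × 7 / 30.4375 = 22.5 months for the last facilitated treatment request, and 1 + 11 = 12 weeks of varenicline.

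**Routes by which an SAE could reach the study team**

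| Route | Source | Scheduled or searched? |
|---|---|---|
| Calls at 3, 12 and 26 weeks post-quit | Participant | Scheduled; asks about AEs |
| Three counseling calls, intensive treatment only | Participant | Scheduled; asks about AEs; ends 1 week post-quit |
| Care Manager contacts (outreach to 22 months, half the sample) and semi-annual interviews (to 24 months, all) | Participant volunteers the event | Contact scheduled; no AE questioning specified |
| EHR messages between Care Managers and primary care providers, which may concern SAEs | Either party | No trigger or search specified |
| EHR extract | Health-system records | Extracted, with no stated safety use |

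The 1–3 contacts collected at baseline are for locating participants. No use of them to report events is described.

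**Missed calls, if unrelated to the event.** Take 25% missing per post-quit call. This is borrowed: the plan gives it for Aim 1 follow-up data, not for these calls. Because each call asks back to treatment start, any later completed call can recover an earlier event.

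- No completed post-quit call, misses independent: 0.25³ = 0.0156, or 1.6% of treated participants.
- No completed post-quit call, same people missing all three: 25%.
- With independent misses, an event before week 3 is lost in 1.6% of cases. Between weeks 3 and 12 the figure is 0.25² = 6.25%. After week 12, when only one call remains, it is 25%.

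These figures exclude any non-response caused by the event. The documents give nothing from which to size that part. For a death, participant report fails by definition from that point on.

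**Births after conception on study medication.** Section F gives varenicline from week −1 to week 11 relative to the quit day, and combination NRT from week 0 to week 12. Assumption, not in the documents: term is 37–42 weeks of gestation, which is 35–40 weeks after conception.

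- Varenicline: −1 + 35 = week 34, to 11 + 40 = week 51.
- Combination NRT: 0 + 35 = week 35, to 12 + 40 = week 52.

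Together this is weeks 34–52, that is 8 to 26 weeks after the last scheduled AE call.

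**Late starters.** A request at week 98 with a quit day 1 week later puts the 26-week call at 98 + 1 + 26 = 125 weeks, or 125 × 7 / 30.4375 = 28.7 months. The Design Overview caps participation at 27 months. The EHR extraction period of up to 4 years post-enrollment still covers this date.

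**The case against.** The strongest reply is that detection is wider than the scheduled calls. That is correct. A reader might infer that SAEs can surface only on calls ending at 26 weeks, and the documents do not support that. Volunteered reports are captured at every later contact, and Care Managers are health-system employees who can exchange messages with providers about SAEs. What remains is that both routes are passive.

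A reader might also take the 25% to mean that a quarter of SAEs would be missed. It is closer to a ceiling when misses are unrelated to the event, because of the look-back to treatment start. For events before week 12, which covers nearly all time on medication, independent misses give 1.6% to 6.25%.

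Nor does every term birth fall after the last call. Pregnant women may enroll and use standard care. One who is already 37 − 26 = 11 weeks or more pregnant at the quit day could deliver at term by week 26. For study medication, the plan excludes pregnancy, requires contraception and adds a chart check. A conception at week 12 is 26 − 12 = 14 weeks along at the final call, so the pregnancy itself could be reported there even though its outcome could not.

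Finally, restricting active assessment to treatment episodes is a reasoned choice for approved medications under provider review. The point here does not contest that choice. It concerns detection inside the window that the plan itself sets. The uploaded adverse event protocol was not available and could contain more than the protocol describes.

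**Conclusion.** The concern holds as a gap in ascertainment. The protocol names death, hospitalization and birth defects as SAEs and describes no systematic means of finding them beyond participant report, with the last scheduled AE call at 26 weeks post-quit. Followed as written, the DSMC data can lose serious events selectively.

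The part that can be sized is 1.6% to 25% of treated participants with no completed post-quit call. It rests on the borrowed 25% and on misses unrelated to the event. Event-related loss adds to this by an unknown amount. The placing of term births at weeks 34–52 applies to conceptions on study medication and rests on the stated gestation range.

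The documents do not show that the EHR extract already holds all the named events. Utilization supports hospitalizations. Whether deaths are included depends on the List of EHR Data to Be Extracted, which is a separate upload. No extraction of, or consent for, infant records is mentioned.

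**What to change.** For every participant who starts treatment, in either access condition, search the semi-annual EHR utilization extract for hospitalizations and any recorded death from treatment start to 26 weeks post-quit. For late starters, use the longer extraction period. Send flags through the existing adverse event protocol and give them to the DSMC as a separate EHR-ascertained line. Because the search is the same in both access conditions, this line also avoids the imbalance from the three extra AE calls in intensive treatment.

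Amend the Design Overview, the risk-minimization text in section H and the adverse event reporting part of the Data Safety and Monitoring Plan to name safety as a use of EHR data. State there how volunteered reports and provider messages about SAEs are handled. Check that the Study Information Sheet covers this use; the telephone consent in section B already covers EHR data for research. Confirm against the List of EHR Data to Be Extracted whether death is included. Reconcile the 98-week limit on treatment requests with the 27-month maximum so that the 26-week call has a defined place.

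The cost is a few protocol sentences, a consent-wording check, one further query on each extract and a short review of flagged events that prove unrelated. Events treated outside the two health systems would still be missed, and a semi-annual extract serves periodic review better than expedited reporting. Birth-outcome flagging is not part of this inexpensive change; it would need its own consent and data arrangements.
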